Multiple scans would allow for estimates of day-to-day variation of the GTV, CTV and OAR (Figure 1a+b). This would provide more correct margins for construction of populations based PTV and the possibility for individual patient based margins to account for the day-to-day variation of the specific GTV, CTV and OAR (Figure 1d). This may be even more important with the introduction of intensity modulated radiation therapy (IMRT) and advanced image guided radiation therapy (IGRT), as the administered dose is highly conformal and precisely delivered. Incorrect margins increase the risk of inadequate dose coverage of PTV and overdose of OAR – both potentially damaging.

Several studies have shown that anisotropic motion and shape variation of the rectum occurs during a CRT course⁷⁻⁹. These variations depend on the region of the CTV and also on the gender of the patient. In addition to the random day-to-day variation, systematic change in position and shape of both CTV and OAR may occur. Studies have shown an average reduction of the rectal volume of 57 % during radiotherapy treatment (RT), with almost all reduction occurring within the first 9 fractions¹⁰.

These studies support that a more detailed knowledge of organ motions and changes during treatment would allow for more correct PTV margins and an adaptive CRT approach. This could result in an improved dose coverage of the PTV or potentially sparing OARs. A sparing of OARs could facilitate a potential dose escalation to the GTV or CTV with a reduction in treatment toxicity.

[figure not shown]

Figure 1: Construction of CTV-PTV margin. Yellow=OAR, Red=GTV, Green=CTV and Blue=PTV margin. Figure 1a and 1b illustrate the difference in motion of GTV/CTV for two different patients. Figure 1c shows a population based PTV margin taking into account target motion for both patients. Figure 1d shows the reduced margin using an individual margin construction.

The aim of this feasibility study is to address the impact on radiotherapy planning from systematic and random day-to-day variation in position and shape of the GTV and CTV in patients with rectum cancer using additional MRI scans before and during radiotherapy.

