Current standard treatment for rectal cancer in the department is based on a single planning CT and MRI-scan one week prior to treatment start. Follow-up scans are performed at one year and three years after completions of the RT course. The overall hypothesis is thus that the information from multiple additional MRI scans will allow for more precise, less toxic and more individualized treatment for rectal cancer. Specifically, performing additional MRI scans prior to, during and after treatment, and defining the GTV, CTV and OAR on each scan, will confirm or deny that:

[figure not shown]
- Systematic and random changes in position and shape of the GTV, CTV and OAR can be characterized using additional MRI scans before and during radiotherapy.
- CTV-to-PTV margins for the patient group can be adapted, by characterizing systematic changes in position and shape of CTV during radiotherapy.
- An adaptive CRT strategy will facilitate dose escalation to the GTV without an increase in expected treatment toxicity.
- MRI scans providing morphological and functional data before, during and after CRT will provide information about treatment response and local toxicity.
- It is possible to correlate local toxicity information with registered side effects.

Method

[figure not shown]
Patients will be scanned six times in addition to the standard MRI-scan appointments and follow-up: as part of the RT therapy scan, three-four days after therapy scan, on the first treatment day before the first radiotherapy treatment, after one, two and four weeks of RT, and an additional follow-up scan at two years after RT. DCE-MRI and DWI is not a part of the standard routine MRI-scans of rectal cancer patients in our

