Inclusion and exclusion criteria

Approximately 25 patients are annually referred to the department of oncology for standard preoperative chemoradiotherapy for rectal cancer. Inclusion period is expected to be from June 2018 to June 2020; all patients referred in this time period fulfilling the criteria below will be offered participation in the study.

Inclusion criteria: Patients >18 years referred to standard chemoradiotherapy for locally advanced rectal cancer.

Exclusion criteria:

- Prior surgery in pelvic minor region
- Pacemaker
- Neurostimulator
- Other non MR-compatible implants
- Pregnancy
- Incapable of undergoing MRI
- Incapable of understanding the patient information
- Allergic to contrast agent
- Contraindication for Buscopan
- Reduced renal function (GFR < 50 ml/min)

Patients who cannot tolerate the contrast used for DCE-MRI (due to allergies, contraindications for Buscopan or reduced renal function (GFR < 50 ml/min)) will still be offered inclusion in the study, but without the contrast-based MRI scans.

Benefits and Risks

The MRI examination is not associated with any exposure to ionizing radiation and there are no additional risks involved in comparison to a standard clinical MRI scan with contrast administration. The patient is equipped with earplugs for noise reduction and a manual alarm, which always can be activated during the scans. The total MR examination consists of multiple scans cf. the methods section. The patient will have to spend additional time in the clinic to undergo the MRI scans. All scans will be placed as conveniently as possible to accommodate the patient clinical schedule.

DCE-MRI is not a part of the standard routine MRI-scans of rectal cancer patients in our clinic, and therefore introduce an added inconvenience and small risk. However, these are widely used modalities in other patient-groups e.g. prostate cancer. The DCE-MRI sequence requires the use of intra-venous administered contrast agents using a cannula (venflon). The cannula is placed by the radiographer prior to the MRI scan, using standard sterile technique. This can be associated with mild discomfort and there is a

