low risk of infection around the injection-area. Mild to modest side effects occur in about 2% of the patients. Possible side effects include skin itch, heating sensation, nausea and very rarely vomiting. In about 1 of 1 million patients severe hypersensitivity have fatal consequences, as a result of a collapse of the circulatory system. The department has an established procedure in case of anaphylactic events during use of contrast. This procedure includes an on-call clinician, who will respond promptly to any severe side effects. In less than 1% of the patients renal function may be affected, but this risk will be minimized by performing a blood test of renal function prior to the use of contrast agent.

By participating in the trial, the patients will not necessarily have any clinical benefits. All image analysis will be performed retrospectively, however the additional follow-up scan at second year will be reviewed by a radiologist and therefore a relapse could be detected sooner. The study will foremost contribute to clinical development and research of the use of modern radiological imaging techniques for image-guided radiation therapy.

Statistics

This is an exploratory study. There will be a feasibility check after 14 patients: If the results at this point suggest that the imaging schedule can be adhered to and that a reasonably proportion of eligible patients are willing to participate, the study will continue and is expected to include 25 patients during the inclusion period. If the study has included more than 25 patients before the inclusion period has ended, the study will be closed. If fewer than 25 patients have been included within the inclusion period, the study will be reevaluated. The patients will, in addition to the main analysis, be divided into two sets of subgroups for secondary analysis:

- Gender: women vs. men
- Tumor location (height): High/mid vs. low

Assuming that 50 % of all eligible patients accept participation in the protocol, 25 patients can realistically be enrolled in the proposed time frame and will provide enough information that each subgroup can be analyzed separately as well as together.

Personal privacy

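### Must the projection of 25 patients, and the statement that 25 are enough for each subgroup, be changed?

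*Protocol*

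**What the plan says.** The protocol's section on inclusion and exclusion criteria gives the recruitment base: "Approximately 25 patients are annually referred to the department of oncology for standard preoperative chemoradiotherapy for rectal cancer". It then gives the period: "Inclusion period is expected to be from June 2018 to June 2020". The offer goes to those who qualify: "all patients referred in this time period fulfilling the criteria below will be offered participation in the study". Ten exclusions follow. For three of them (contrast allergy, a contraindication to Buscopan, reduced renal function) the same section adds that these patients "will still be offered inclusion in the study, but without the contrast-based MRI scans".

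The Statistics section draws the conclusion: "Assuming that 50 % of all eligible patients accept participation in the protocol, 25 patients can realistically be enrolled" in the planned time. The same sentence ends by saying that this number "will provide enough information that each subgroup can be analyzed separately as well as together". The subgroups are women against men, and high or mid tumours against low ones. The section calls the study exploratory and the subgroup analyses secondary. It plans a feasibility check after 14 patients, closure if more than 25 are included early, and a re-evaluation if fewer than 25 are included by the end of the period.

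**The concern.** Two things catch the eye.

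First, the 50% is a share of eligible patients, but 25 comes out only when it is applied to all referred patients. Seven exclusions still bar entry, and no eligible share is given. If a real fraction of referrals is ineligible, the expected number falls below 25.

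Second, the protocol asserts that the information is sufficient in each subgroup without giving an expected subgroup size, a variability or a precision. The introduction gives a reason to care, because it says of organ motion: "These variations depend on the region of the CTV and also on the gender of the patient". A reader who takes the statement at face value might treat separate results by gender or tumour height as well estimated, or read the absence of a visible difference as similarity. Low enrolment would shrink the subgroups further, so the two points compound.

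**Working it through.** **Enrolment.** Inputs from the protocol: about 25 referrals a year, June 2018 to June 2020, 50% acceptance among eligible patients. The ineligible share x is not given and is assumed below.

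Expected number = referrals per year × years × (1 − x) × 0.5.

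The protocol's figure, with x = 0: 25 × 2 × 1 × 0.5 = 25. It reproduces exactly. If both Junes count in full (25 months), referrals are 25/12 × 25 = 52.1 and the expected number is 26.0. An expected 25 then needs 25/26.0 = 96% eligible.

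| Assumed ineligible share | Expected, 24 months | Expected, 25 months | Months for an expected 25 | Chance of at least 25 in 24 months (binomial of 50 / Poisson) |
|---|---|---|---|---|
| 0% | 25.0 | 26.0 | 24.0 | 56% / 53% |
| 5% | 23.8 | 24.7 | 25.3 | 42% / 43% |
| 10% | 22.5 | 23.4 | 26.7 | 28% / 33% |
| 20% | 20.0 | 20.8 | 30.0 | 10% / 16% |

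Small movements in the rounded inputs offset the lower rows. With 5% ineligible, an expected 25 needs 25/(2 × 0.95 × 0.5) = 26.3 referrals a year, or 25/(50 × 0.95) = 52.6% acceptance. With 10% ineligible, it needs 27.8 a year or 55.6%.

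The protocol also suggests that x may be small. Its Hypothesis section says that standard treatment in the department already rests on a planning CT and MRI. Four of the seven exclusions that still bar entry concern the ability to have an MRI (pacemaker, neurostimulator, other incompatible implants, unable to undergo MRI). In a population that is scanned routinely, these should remove few patients. The other three are prior pelvic surgery, pregnancy and inability to understand the information.

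**Subgroups.** The smaller part of any two-way split of 25 has at most 12 patients. The 95% limits for a standard deviation are the estimate times √(df/χ² quantile), assuming normality:

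- all 25 patients, one value each (24 df): 0.78 to 1.39;
- 12 patients, one value each (11 df): 0.71 to 1.70;
- 8 patients, in an assumed 17/8 split (7 df): 0.66 to 2.04.

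The 95% half-width of a mean, t × SD/√n, is 0.41 SD for 25 patients, 0.64 SD for 12 and 0.84 SD for 8.

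Random day-to-day variation is better placed. The Method section schedules three scans up to the start of treatment: "as part of the RT therapy scan, three-four days after therapy scan, on the first treatment day before the first radiotherapy treatment". They give 2 df per patient, so 12 patients give 24 df and limits of 0.78 to 1.39. Twelve patients therefore estimate the day-to-day standard deviation as precisely as 25 single values would.

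The wide limits concern variation between patients. The protocol does not name that as a target. Its introduction and its margin endpoint use the word systematic for change in position and shape during radiotherapy. For an average change over the course, the half-width of the mean is the closer guide: about 0.6 SD in each half of a 13/12 split (0.60 and 0.64).

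**The case for a change.** The strongest case for a change runs as follows. The protocol itself separates referred from eligible patients, then reaches 25 only by treating them as the same. Rounding can go either way, but exclusions only lower the number. Even with no exclusions the chance of reaching 25 is little better than even, which strains the claim that the number is realistic. The check after 14 patients and the re-evaluation respond to a shortfall and do not correct the projection. The subgroup statement is not a detail left for an analysis plan, because the protocol asserts sufficiency and gives nothing to support it. Two sentences would put both right at almost no cost.

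Much of this stands as description. The projection has no slack, and the sufficiency statement has no figure behind it. What does not follow is that either is shown to be wrong. An expected number below 25 is not the same as a number out of reach: with 10% ineligible the chance of 25 or more is still about 28 to 33%. The 20% row rests wholly on an assumed rate. The subgroup statement promises separate analysis. It claims no power, no stated precision and no conclusion of similarity, so the intervals above contradict nothing in it.

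**Conclusion.** No change is needed. The projection reproduces from its inputs. It is optimistic by about 0 to 2.5 patients over 24 months if 0 to 10% of referrals are ineligible, and by 5 if 20% are. These rates are assumptions, because the protocol gives none. Recruitment proceeds in the same way whatever share is written down: all eligible patients are offered the study, it closes above 25, and it is re-evaluated below 25. No test, error rate or power calculation rests on the number.

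The subgroup statement is loosely worded. With at most 12 patients in the smaller group, estimates of variation between patients will be imprecise, while day-to-day variation is estimated reasonably well from the repeat scans. In an exploratory study with secondary subgroup analyses, an analyst would report such results descriptively with confidence intervals and would not read a null difference as similarity. If the text is revised for other reasons, the sponsor could state the eligible share and call these analyses descriptive. That would help the reader but would not alter the conduct, the analyses or the conclusions.
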